8.2.1.3 Enrolled Patient Withdrawal and Discontinuations

8.2.1.3.1 Withdrawal Procedures

Early termination from the study occurs when an enrolled patient withdraws consent or the Investigator terminates a patient. The reason for withdrawal will be evaluated and recorded in the case report form (CRF) and source documents. Patients that withdraw will not be replaced.

Patients may withdraw consent at any time. Reason(s) for withdrawal of consent, failure to return for the necessary visits, or termination from the study should be documented. All patients that withdraw early from the study, upon termination should have the Early Termination visit

assessments completed (i.e., End of Study assessments) ([Section 20](#)), if the assessments pose no risk to the patient and the patient allows such assessments.

The Investigator should consult with the Sponsor/medical monitor prior to withdrawing any patient from the study. Since this is a multiple-dose study, once dosed, patients generally should not be terminated by the Investigator and should be followed through the end of Treatment Period 6, unless the patient withdraws consent or is lost to follow-up. In situations where continued participation in certain aspects of the study pose a risk to the patient, with consultation with the medical monitor, the Investigator should discontinue those procedures that pose a risk and should continue to collect data and conduct those assessments that do not put the patient at risk through the end of Treatment Period 6. Patients with compliance issues or major deviations that effect data quality will also continue to be followed through the end of Treatment Period 6 collecting as much data on the patient as possible, unless otherwise indicated by the Sponsor.

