5.6. Protocol Deviations

All protocol deviations related to study inclusion or exclusion criteria, conduct of the trial, patient management, dosing, and sampling procedures or patient assessment will be listed. The list of protocol deviations will be reviewed by the Sponsor, the principal investigator, the study statistician and the study pharmacokineticist and finalized before database lock. Determination of whether the deviation is major or minor, or has impacts on primary efficacy assessment will be based on the biasing impact of the deviation on the safety and efficacy data. Major protocol deviations affecting the primary efficacy assessments include: 1) major protocol deviations that lead to premature study drug discontinuation; 2) major protocol deviations that lead to patients receiving study drug treatment in treatment periods 3 or 6 that they would not otherwise have received (such as incorrect application of the protocol stopping rules that allow a patient to continue dosing despite having met the stopping criteria); and 3) protocol deviations that involve out of window sampling of SUA due to a) visits occurring outside of the protocol visit window for dosing days (where dosing days refer to dosing visits of patients still on study drug who have not previously been withdrawn from study drug) in Treatment period 3 and 6, b) visits occurring outside of the protocol visit

This document is confidential.

window for visits within TP3 or TP6 scheduled 1 week prior to the dosing days, c) visits occurring outside of the protocol visit window for TP6 D21 for patients who have not been withdrawn from study drug and for dosing day TP4D0, or d) visits occurring 35 days or more beyond TP6D0 for the TP6D28 visit for patients who have not been withdrawn from study drug, where the protocol visit window above refers to the current protocol window allowed at the time of analysis. Major protocol deviations affecting the primary efficacy assessments will be reviewed and determined periodically during clinical and medical review of protocol deviations during the study.

Protocol deviations related to Covid-19 will be identified and flagged.

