Missing scheduled assessments of SUA will be imputed as follows: If SUA is missing at day 0 (predose) for periods 3, 4 and 6 and day 28 for period 6 in the SEL-212 cohort, baseline SUA will be used for calculation. If SUA is missing at day 0 (predose) for periods 3, 4 and 6 and day 28 for period 6 or day 14 (pre-dose) for treatment periods 3 and 6 in the Krystexxa cohort, baseline SUA will be used for calculation. Day 0 predose time point is the same as day 28 of previous treatment period. For example, period 4 predose is same as period 3 day 28. If SUA is missing at the post-dose timepoint on dosing days (ie post-treatment on Day 0 in SEL-212 cohort or post-treatment on either D0 or D14 in Krystexxa cohort) in either Treatment period 3 or 6 or is missing at Day 21 of treatment period 3 or 6 for the SEL-212 cohort for a patient, it will be imputed by the mean of the available assessments at the respective time from the prior Treatment Periods (ie from Treatment periods 1 and 2 for missing data in TP3 and from Treatment periods 1 to 5 for missing data in TP6) of this patient. Missing SUA assessments at Day 7 and Day 14 in the SEL-212 cohort and missing SUA assessments at Day 7 and 21 in the Krystexxa cohort will not be imputed, but SUA time curve will be determined by interpolation.

This document is confidential.

If the duration of the Treatment Period 3 or 6 has been extended by more than 6 days beyond its nominal 28 day duration due to study visits occurring beyond their protocol windows, the corresponding TP4 day 0 (predose) or TP6 day 28 value will be imputed by the baseline value for the patient at the timepoint of 28 days after the previous Day 0 timepoint (TP3 or TP6) and only those SUA values drawn within 28 days of the respective day 0 (ie. TP3 or TP6) will be used in calculating the proportion of time that the SUA level is below 6 mg/dL.

The primary estimand will take into consideration the treatment policy strategy, ie, Treatment Period 3 and 6 assessments will be considered for all patients in ITT independently whether the patient has completed the study treatment or has terminated the study treatment early. If a subject withdraws from study before completing period 6 or is put back on ULTs, the subject will be considered as a non-responder for the primary efficacy endpoint. The return of ULTs is a confounding factor for subsequent SUA efficacy.

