The estimator for the comparison between the treatment groups is defined as the difference in the proportion of responders between patients receiving SEL-212 versus those receiving KRYSTEXXA® during Treatment Periods 3 and 6. The statistical testing will be performed confirmatory using the Cochran-Mantel-Haenszel (CMH) test – considering the randomization stratum of tophus presence (yes/no) – with a one-sided type 1 error rate $\alpha = 5\%$. In addition, 90% two-sided confidence intervals for the overall treatment difference between SEL-212 and KRYSTEXXA® treatment groups without stratification will be computed. The analysis of the estimands will be carried out based on the ITT primarily. Supportive analyses will be performed on the mITT and the PP.

A logistic regression model to compare treatment difference controlling for presence of tophus will be performed as supportive analysis.

In addition, a sensitivity analysis will be performed as below for the primary endpoint:

- If a subject withdraws from study treatment before completing period 6 due to stopping rules met for treatment, the subject will be considered as a non-responder for the primary efficacy endpoint.
- If a subject withdraws from the study before completing period 6 or the study terminates prior to a subject completing period 6, the primary efficacy endpoint is based on SUA assessment for period 3 where $T1$ be the total time interval in hours for Treatment Period 3 of which $W1$ hours is the time interval during which SUA level is < 6 mg/dL:

$$\text{Percentage (p)} = \frac{W1}{T1} \times 100$$

Summary tables of the percentage of responders (patients who achieve and maintain reduction of SUA < 6 mg/dL for at least 80% of the time) will be provided by treatment group. Additionally, a summary table with the total time a patient has SUA values < 6 mg/dL will be provided for treatment period 3 and treatment period 6 by treatment group.

Summary tables of the actual values and change from baseline for SUA results will be provided for each scheduled sampling time point by treatment group.

This document is confidential.

Additionally, mean SUA level, reduction in mean SUA and percent reduction in mean SUA from baseline during Treatment Periods 3 and 6, during Treatment 3, and during Treatment Period 6 will be summarized by treatment group respectively and will be compared for treatment difference using ANOVA model with presence of tophus and treatment group as fixed factors

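### SAP 7.1 lets earlier on-drug Day 21 values replace missing off-drug values in the SEL-212 arm, and specifies no check for patients withdrawn from drug for an adverse event

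*SAP*

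**What the plan says.** **The fill.** SAP 7.1 has this rule for SUA: "missing at Day 21 of treatment period 3 or 6 for the SEL-212 cohort for a patient, it will be imputed by the mean". That mean uses the same patient's values at that time point in earlier periods: Periods 1 and 2 for Period 3, and Periods 1 to 5 for Period 6. Nothing in the rule depends on whether drug was given in the period being filled. In the KRYSTEXXA arm a missing Day 14 pre-dose value takes baseline, and a missing Day 21 value is interpolated.

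**Who is analysed.** The primary estimand counts Period 3 and 6 data "independently whether the patient has completed the study treatment or has terminated the study treatment early". Protocol 7.4.1.1 keeps patients withdrawn from SEL-212 in visits to the end of Period 6. Protocol 8.2.1.3.1 says that, once dosed, "patients generally should not be terminated by the Investigator and should be followed through the end of Treatment Period 6". In the primary analysis only leaving the study or returning to urate-lowering therapy (ULT) forces non-response.

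**Checks specified.** The first sensitivity bullet in SAP 7.1 concerns withdrawal from treatment "due to stopping rules met for treatment, the subject will be considered as a non-responder for the primary efficacy endpoint". The second scores on Period 3 alone those who leave the study or whose study ends early. SAP 5.6 lists, as grounds affecting the per-protocol (PP) set, "major protocol deviations that lead to premature study drug discontinuation" and visits "outside of the protocol visit window for TP6 D21 for patients who have not been withdrawn from study drug". Protocol 13.4.1 promises sensitivity analyses using different imputation approaches and leaves the details to the SAP.

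**The concern.** A treatment-policy endpoint should reflect SUA after drug is stopped. If a patient is off drug and the Day 21 sample is missing, the SAP inserts values from when the drug was working. Those values are low almost by construction: under protocol 7.4.1.1, an in-window Day 21 value that allows the next dose is at most 1.0 mg/dL in Period 1 and at most 6.0 mg/dL in later periods. Where off-drug SUA is 6 or above, the fill can only add time below 6.

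At stake is whether an off-drug SEL-212 patient can be scored a responder on the confirmatory endpoint, in one arm only, with no specified analysis that would show it.

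**Working it through.** **Which analyses reach the patient.** Take a SEL-212 patient withdrawn from drug for an adverse event who stays in the study and off ULT.

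- First sensitivity bullet: stopping-rule withdrawals only, so no.
- Second bullet: leaving the study or study termination only, so no.
- mITT and the logistic model: same responder score.
- PP: a patient who keeps attending meets the 65% visit rule (SAP 5.5). The Period 6 Day 21 item in 5.6 is confined to patients not withdrawn. The discontinuation item needs a major deviation that caused withdrawal. PP may therefore not remove the patient.
- Central-laboratory analysis (SAP 7.4.1): changes the data used, not the rule.
- ULT return: discretionary, and allowed 60 days after the last dose. For a last dose at Period 5 Day 0 (nominal day 112), 112 + 60 = 172, after Period 6 ends on day 168. For a last dose at Period 4 Day 0, 84 + 60 = 144, which is Period 6 Day 4.

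**Inputs.** From SAP 7.1: linear interpolation, 28-day periods, and response at 80% or more of pooled time. Assumed, because the documents give no such values: on-drug SUA f = 0.3; Period 3 fully below 6; Period 6 Day 28 observed; no ULT, post-dose or unscheduled value; last dose at Period 5 Day 0 with all five earlier Day 21 values at 0.3; off-drug SUA S = 7, 8 or 10.

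**Formulae.** A line between f and S lies below 6 for the fraction r = (6 − f)/(S − f): 5.7/6.7 = 0.851, 5.7/7.7 = 0.740 and 5.7/9.7 = 0.588. Pooled % = (28 + Period 6 days below 6)/56. Response needs 0.80 × 56 − 28 = 16.8 days in Period 6.

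**Profile 1: Period 6 Day 0 still 0.3, SUA = S from Day 7.** Percentages are for S = 7 / 8 / 10.

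| Period 6 visits missing | SAP fill | Interpolation |
|---|---|---|
| Day 21 | 21r: 81.9 / 77.8 / 72.0 | 7r: 60.6 / 59.3 / 57.3 |
| Days 14, 21 | 28r: 92.5 / 87.0 / 79.4 | 7r: 60.6 / 59.3 / 57.3 |
| Days 7, 14, 21 | 21 + 7r: 98.1 / 96.8 / 94.8 | 28r: 92.5 / 87.0 / 79.4 |

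Example: S = 7 with Day 21 missing gives 21 × 0.851 = 17.9 days and (28 + 17.9)/56 = 81.9%. One missed Day 21 makes a responder when 21r ≥ 16.8, so r ≥ 0.8 and S ≤ 0.3 + 5.7/0.8 = 7.4.

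**Profile 2: SUA = S throughout Period 6, including Day 0 (true value 50%).** Only Day 21 missing: 14r gives 71.3 / 68.5 / 64.7, never a responder because 14r < 16.8. Days 14 and 21 missing: 21r gives 81.9 / 77.8 / 72.0. Days 7, 14 and 21 missing: 28r gives 92.5 / 87.0 / 79.4, a responder up to S = 0.3 + 5.7/0.6 = 9.8.

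**Slower rise.** With Period 6 Days 0, 7, 14 and 28 at 3, 5, 7 and 8 and a fill of 0.5, interpolation gives 7 + 3.5 = 10.5 days (68.8%). The fill adds 7 × 5.5/6.5 + 7 × 5.5/7.5 = 11.1 days (88.5%).

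**Limits.** Earlier withdrawal weakens the fill, because off-drug Day 21 values enter the mean. With one of five at 8, f = (4 × 0.3 + 8)/5 = 1.84. The Period 3 fill alone cannot make a pooled responder if Period 6 stays above 6: the maximum is 28/56 = 50%.

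**Scale.** With 75 patients per arm, one false SEL-212 responder adds 1/75 = 1.33 percentage points to the difference.

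**The case against.** The strongest reply is that the exposed group is very small. The patient must be on SEL-212, withdrawn for a reason outside the stopping rule, still attending, off ULT, controlled in Period 3 and missing Period 6 Day 21. In Profile 1 one missed visit matters only up to SUA 7.4, while eligibility needs at least 7 at Screening. Profile 2 also needs SUA to jump from 0.3 at Period 5 Day 21 to its off-drug level seven days later, which the documents do not support. All of this stands and limits the size of the point. It does not supply the missing on-drug condition.

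Several stronger readings are tempting but not supported:

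- *No test is planned at all.* Protocol 13.4.1 does plan alternative imputation. The gap is that the SAP specifies none.
- *PP would repeat the false score.* It may. SAP 5.6 grades deviations by their biasing impact, so missed visits could be classed as major.
- *The while-on-treatment estimand promised in the protocol would have exposed this.* It would set aside off-drug Period 6 data and score these patients mainly on a controlled Period 3.
- *The SAP's COVID-19 text predicts these gaps.* It anticipates patients not completing or the study stopping early, not isolated missed Day 21 samples.
- *The post-dose fill also lowers off-drug curves.* That fill begins "If SUA is missing at the post-dose timepoint on dosing days" and describes a post-treatment sample. SAP 5.6 uses dosing days in the sense "where dosing days refer to dosing visits of patients still on study drug who have not previously been withdrawn from study drug". Reaching withdrawn patients is the strained reading, although 7.1 does not exclude it in words.

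**Conclusion.** The point holds as a defect in a stated rule that should be fixed. SAP 7.1 can credit off-drug time as controlled in the SEL-212 arm, and none of its specified analyses checks this for adverse-event and similar withdrawals who stay in the study off ULT.

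Under the stated assumptions, a single missed Period 6 Day 21 makes a false responder only if Period 6 Day 0 is still controlled and, when SUA is at its off-drug level by Day 7, that level is at most about 7.4 (81.9% against 60.6% at SUA 7). A slower rise can flip a patient whose SUA ends higher. With Days 14 and 21 both missing in Profile 1, the fill gives 87.0% against 59.3% at SUA 8. The Period 3 fill cannot create a pooled responder alone, but it can raise the Period 3 secondary endpoint and the Period 3 sensitivity score.

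A reader might infer that the trial result is biased towards SEL-212. The documents do not support that: they give no missingness or adverse-event withdrawal rate, so the number affected and the net direction are unknown. Confidence is high for the gap in the wording, not for its effect on the result.

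**What to change.** 1. In SAP 7.1, limit the Day 21 prior-period mean to patients still on study drug in that period. Otherwise interpolate between observed values, scheduled or unscheduled.
2. Specify the alternative-imputation sensitivity analysis that protocol 13.4.1 promises, in both arms, with interpolation and with baseline fill at Day 21 as the worst case. Interpolation alone is not enough. In Profile 1 at SUA 8 with Days 7, 14 and 21 all missing it still gives 87.0%, whereas baseline fill (baseline 8) gives 21r, or 77.8%. At SUA 7 (baseline 7) even that gives 81.9%, so report how many patients have such gaps.
3. Optionally, add one sentence saying that the post-dose fill applies, in both arms, only when an infusion was given.

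The primary analysis need not use one common rule for SEL-212 Day 21 and KRYSTEXXA Day 14. The cost is minor SAP wording and programming, with no new data.

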7.4.1 Safety Criteria for Adjustment or Stopping Doses

7.4.1.1 SEL-212

A patient randomized to treatment with SEL-212 will be withdrawn from study drug for meeting the following stopping rule:

- In the SEL-212 arm: SUA level > 1.0 mg/dL measured at the Day 21 visit of Treatment Period 1 or SUA level > 6.0 mg/dL at the Day 21 visit of Treatment Periods 2, 3, 4, or 5

The window for all Day 21 visits is -2/+1 days.

If a Day 21 visit SUA value drawn within the protocol window is not available, but if a SUA value drawn at an unscheduled visit after the Day 21 window is available prior to dosing that is ≤ 1.0 mg/dL during Treatment Period 1 or ≤ 6.0 mg/dL during Treatment Periods 2, 3, 4, or 5, the patient will not be required to be withdrawn from study drug and may be eligible to receive their subsequent dose.

If 1) a Day 21 visit SUA value drawn within the protocol window is not available and no subsequent SUA results are available or 2) a Day 21 visit SUA value drawn within the protocol window is not available and a subsequent SUA drawn at an unscheduled visit after the Day 21 window is > 1.0 mg/dL during Treatment Period 1 or > 6.0 mg/dL during Treatment Periods 2, 3, 4, or 5, then the patient will be withdrawn from study drug based on the protocol deviation.

If withdrawn from study drug, the patient will continue study visits to the end of Treatment Period 6. At the discretion of the Investigator, the patient will be permitted to return to urate lowering therapy 60 days after the patient's last study drug treatment. Urate lowering therapy shall not be SEL-212 or KRYSTEXXA.

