9.2.1 Uric Acid Lowering Therapy

Uric acid lowering therapy (ULT) including, but not limited to allopurinol, febuxostat (Uloric[®]), probenecid, lesinurad (Zurampic[®], Duzallo[®]), and benz bromarone ULT, are not permitted for use during the study. Patients will undergo a ULT washout period prior to dosing with study drug according to the schedules described in [Section 20](#).

Patients cannot have any prior exposure to or be presently be taking any experimental or marketed uricase therapy, as defined in Exclusion Criterion 1 ([Section 8.2](#)).

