4.2. Secondary Efficacy Endpoints

Secondary Endpoints:

- Reduction of mean SUA in patients on SEL-212 vs. KRYSTEXXA® as computed by subtracting baseline SUA level from the mean SUA (area under the SUA time curve) during Treatment Period 3 and Treatment Period 6
- Percent reduction of mean SUA in patients on SEL-212 vs. KRYSTEXXA® as computed as the mean SUA level during treatment period (area under the SUA time curve) minus baseline SUA level divided by baseline SUA level multiplied by 100 during Treatment Period 3 and Treatment Period 6
- Percentage of patients on SEL-212 vs. KRYSTEXXA® who achieve and maintain reduction of SUA < 6 mg/dL for at least 80% of the time during Treatment Period 6
- Percentage of patients on SEL-212 vs. KRYSTEXXA® who achieve and maintain reduction of SUA < 6 mg/dL for 100% of the time during Treatment Period 6
- Reduction of mean SUA in patients on SEL-212 vs. KRYSTEXXA® as computed by subtracting baseline SUA level from the mean SUA (area under the SUA time curve) during Treatment Period 6
- Percent reduction of mean SUA in patients on SEL-212 vs. KRYSTEXXA® as computed as the mean SUA level during treatment period (area under the SUA time curve) minus baseline SUA level divided by baseline SUA level multiplied by 100 during Treatment Period 6
- Percentage of patients who achieve and maintain reduction of SUA < 6 mg/dL for at least 80% of the time during Treatment Period 3
- A summary table of the number and percentage of patients who achieve and maintain reduction of SUA < 6 mg/dL for 100% of the time during Treatment Period 3 will be provided by treatment group.
- Reduction of mean SUA in patients on SEL-212 vs. KRYSTEXXA® as computed by subtracting baseline SUA level from the mean SUA (area under the SUA time curve) during Treatment Period 3
- Percent reduction of mean SUA in patients on SEL-212 vs. KRYSTEXXA® as computed as the mean SUA level during treatment period (area under the SUA time curve) minus baseline SUA level divided by baseline SUA level multiplied by 100 during Treatment Period 3
- Percent of patients on SEL-212 vs. KRYSTEXXA® in pre-dose SUA values > 6 mg/dL during Treatment Periods 2-6. The pre-dose SUA is collected on the dosing day prior to the dosing administration or it is collected at the visit where dosing would have occurred had the patient not

This document is confidential.

Statistical Analysis Plan

Sponsor: Selecta Biosciences

Protocol No.: SEL-212/202

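### The rule that counts return to urate-lowering therapy as non-response covers only the primary endpoint, leaving the TP6 response and mean-SUA secondary endpoints without one

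*SAP*

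**What the plan says.** SAP 7.1 adopts a treatment-policy strategy for the primary estimand and then makes an exception. A patient put back on ULT is "considered as a non-responder for the primary efficacy endpoint. The return of ULTs is a confounding factor for subsequent SUA efficacy". The second of those sentences is the SAP's own reason for the rule.

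Protocol 7.4.1.1 (SEL-212) leaves the choice to the investigator: "the patient will be permitted to return to urate lowering therapy 60 days after the patient's last study drug treatment". Protocol 7.4.1.2 gives the same allowance for KRYSTEXXA. Follow-up does not stop: "If withdrawn from study drug, the patient will continue study visits to the end of Treatment Period 6".

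The secondary SUA endpoints are in SAP 4.2. SAP 7.2.1 tests TP3 response at 80%, TP6 response at 80% and 100%, and pre-dose SUA above 6 mg/dL, each at one-sided 5%. TP3 response at 100% is summarised by arm. SAP 7.1 compares mean SUA and percent reduction between arms by ANOVA. None of these passages mentions ULT, and neither do SAP 5.9 (missing data) or Protocol 13.4.2. For the pre-dose endpoint, off-drug values are used deliberately: after withdrawal, "it is collected at the visit where dosing would have occurred".

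Protocol 9.2.1 says that ULTs "are not permitted for use during the study", and the assessment schedules in Appendices A and C have patients abstain after washout.

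**The concern.** The SAP's reason for the rule, that ULT confounds later SUA, is general, but the rule is limited to one endpoint. For the rest, a programmer following the text would use every SUA value collected, including values lowered by a drug that is not under study. One patient could then be a primary non-responder because of ULT and a TP6 responder because of ULT.

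The TP6-only endpoints are more exposed than the primary. The primary pools TP3 and TP6, so a patient with no controlled time in TP3 and full control in TP6 reaches only (0 + 28)/(28 + 28) = 50%, and fails the 80% threshold with or without the rule. The TP6 endpoints look at TP6 alone and have no such cushion.

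At stake is what the secondary SUA comparisons mean, and whether they agree with the primary.

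**Working it through.** **The plan's own figure.** Inputs from Protocol 13.1: 65% vs 44%, one-sided 5%, 80% power. With pooled variance,
n = [1.645·√(2·0.545·0.455) + 0.842·√(0.65·0.35 + 0.44·0.56)]² / 0.21² = 68.5, rounded up to 69 per group, as stated. Power at the 75 randomized per arm is 83.1%. Nothing here changes that figure.

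**When ULT can overlap the analysis windows.** Nominal days: TP3 is Days 56–84 and TP6 is Days 140–168. Earliest ULT day = last dose day + 60.

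| Last dose | ULT from | Share of TP3 | Share of TP6 |
|---|---|---|---|
| Day 0 | Day 60 | 24/28 = 85.7% | 100% |
| Day 14 (KRYSTEXXA) | Day 74 | 10/28 = 35.7% | 100% |
| Day 28 | Day 88 | 0 | 100% |
| Day 56 | Day 116 | 0 | 100% |
| Day 70 (KRYSTEXXA) | Day 130 | 0 | 100% |
| Day 84 | Day 144 | 0 | 24/28 = 85.7% |
| Day 98 (KRYSTEXXA) | Day 158 | 0 | 10/28 = 35.7% |
| Day 112 or later | Day 172 or later | 0 | 0 |

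Dosing windows move these boundaries by a few days.

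- *TP6.* Full coverage is possible for last doses up to Day 56 (SEL-212) or Day 70 (KRYSTEXXA). After a last dose on Day 84, ULT can start on Day 4 of TP6. The 100% endpoint is then out of reach if the Day 0 value is 6 or more, and the 80% endpoint needs SUA below 6 by Day 5.6 (20% of 28 days).
- *TP3.* The SEL-212 rule can stop a patient after one dose, which allows 85.7% of TP3 on ULT. The KRYSTEXXA rule excludes the first pre-dose value and needs two consecutive ones, so a patient stopped by it normally has a last dose on Day 14 or later and at most 35.7% of TP3 on ULT.
- *Pre-dose SUA above 6.* A KRYSTEXXA patient is stopped because of such values. A SEL-212 patient has would-be dosing visits 28 and 56 days after the last dose, both before day 60. If the endpoint means any occurrence in TP2–6, later ULT rarely changes it. The SAP does not say whether it means any occurrence or per visit.

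**Size.** The documents give neither a restart rate nor a control rate, so both are assumed. Failures are taken as 1 − 0.65 = 35% and 1 − 0.44 = 56%.

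Inflation = failure share × share restarting ULT × share of those below 6.

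- SEL-212: 35% × 20% × 10% = 0.7 points, up to 35% × 40% × 30% = 4.2 points.
- KRYSTEXXA: 56% × 20% × 10% = 1.1 points, up to 56% × 40% × 30% = 6.7 points.

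**Direction.** With equal shares in both arms, the difference shrinks by 1.1 − 0.7 = 0.4 up to 6.7 − 4.2 = 2.5 points. With the low shares in SEL-212 and the high ones in KRYSTEXXA, it shrinks by 6.7 − 0.7 = 6.0. With the reverse, it grows by 4.2 − 1.1 = 3.1.

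**The case against.** Five arguments can be made for leaving the text alone.

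1. *SAP 7.2.1 already carries the rule over, because it likens these comparisons to the primary.* The likeness is tied to the CMH test and its stratum; intercurrent events are not mentioned. It also cannot reach mean SUA, for which non-response has no meaning. This does not stand.

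2. *Treatment policy is a legitimate strategy, and post-withdrawal SUA is collected on purpose.* It would be legitimate if stated for the secondaries. The SAP states it for the primary and overrides it there for ULT. What stands is that no single handling is compulsory for the continuous endpoints. Setting post-ULT values to baseline, for instance, would be a debatable worst-case choice.

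3. *Few of these patients would be controlled on ULT.* Inclusion criterion 5 requires inadequate control on xanthine oxidase inhibitors or a contraindication to them. This stands as a limit on size, not on the gap.

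4. *The exposed group is smaller than all failures.* This stands. Late failures have no exposure, and the 35% and 56% belong to the pooled primary, not to TP6 alone. If, say, only half of failures stopped early enough, 40% of all failures restarting would mean 80% of those eligible.

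5. *The consequence is limited.* The primary is protected, SAP 7.2 sets no hierarchy among secondaries, and Protocol 13.4.1 only presents mean SUA by group. This stands and keeps the point below the primary analysis in importance.

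A reader might also infer that the gap favours SEL-212, or that it always dilutes the difference. The documents support neither. Unequal restart is plausible, because the stopping rules differ and restart is at the discretion of an investigator who knows the arm, but no rate is given.

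**Conclusion.** The gap is real and worth closing; the primary analysis is unaffected. As written, a patient last dosed by about Day 56 (SEL-212) or Day 70 (KRYSTEXXA) can be on ULT throughout TP6 and count as a responder in both TP6 endpoints, and ULT-lowered values enter mean SUA and percent reduction. Exposure is slight in TP3, nil for last doses on Day 112 or later, and small for the pre-dose endpoint on the any-occurrence reading. It would be wrong to conclude that every secondary SUA endpoint is materially distorted.

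The ranges of 0.7–4.2 points (SEL-212) and 1.1–6.7 points (KRYSTEXXA) rest on assumed shares and on the sample-size response rates standing in for TP6 rates. They illustrate scale and are not estimates. The sign of the bias in the difference is open.

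The conflict between Protocol 9.2.1 with the schedules and Protocol 7.4.1.1 and 7.4.1.2 is a separate point. It needs reconciling, but the analysis gap does not depend on it.

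**What to change.** In SAP 7.2.1, extend the existing rule to the TP3 and TP6 endpoints at 80% and 100%: a patient put back on ULT before or during a period is a non-responder for that period.

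For mean SUA and percent reduction (SAP 4.2 and 7.1), name the strategy for values after ULT restart and add a sensitivity analysis under an alternative handling.

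Separately, reconcile the ban in Protocol 9.2.1 and the abstention line in Appendices A and C with the allowance in 7.4.1.1 and 7.4.1.2. Which text should prevail is for the sponsor to settle.

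The cost is a few sentences of SAP text, a little programming and slightly lower reported secondary response rates. The sample size does not change, and ULT use should already be captured, since concomitant medications are recorded throughout the study.
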